9.1 STATISTICAL HYPOTHESES AND PROPOSED ANALYSES

Specific Aim 1. Descriptive statistics (frequencies, min, max, mean, standard deviation) and contingency table analysis will be performed to identify any possible coding errors. Data inconsistencies identified will be sent back to sites for correction. We will calculate the proportion and exact 95% confidence interval (CI) of CASH cases among all CA cases at each SCA site and overall. Baseline characteristics will be summarized using chi-square tests for categorical variables and t-tests for continuous variables. EQ-5D measures are scored on the T-score metric, with a mean of 50 and standard deviation (SD) of 10 in a referent population (mild, moderate, and severe impairment is defined as 0.5-1.0 SD, 1.0-2.0 SD, or 2.0+ worse than the mean, respectively). Spearman correlation coefficients will be calculated between mRS and Euro-QoL and PROMIS29 scales, and mean scores of Euro-QoL and PROMIS29 will be stratified by mRS levels. This analysis will allow us to determine ceiling effects of scores and how well the Euro-QoL and PROMIS29 data are distributed in CASH cases. Functional and QOL scores shall also be analyzed by pre-defined subgroups (sex, genotype and lesion location), to inform stratification or the need for adaptive randomization in clinical trials.

Specific Aim 2. This will follow the same design for QSM and DCEQP data acquired using these phantoms. A $p<0.05$ will be considered a failure, or significant non-zero difference. The accuracy of QSM and DCEQP values will be assessed at each of the sites participating in the FUBV arm by estimating the coefficient of determination r^2 between the observed and known phantom values, with $r^2 \geq 0.95$ needed to validate accuracy of each technique³⁵. The Pearson's correlation coefficients r of the FUBV subjects will also be compared using Fisher transformation. The precision of QSM and DCEQP measurements will be tested by comparing two separate measurements acquired at each site, using a paired t-test (7 ferumoxytol concentrations acquired twice by QSM, and 7 permeability values simulated with the phantom twice by DCEQP). The reproducibility of phantom measurements will be evaluated by comparing the QSM and DCEQP simulation values acquired at New Mexico and Mayo Rochester against the values obtained at Chicago, and one another, using a two-sample t-test.

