univariable and multivariable logistic regression and reported as odds ratios and 95% CIs. Depending on the number of recurrent SH over the 2-year period, we may analyze re-bleeds as a continuous outcome and the associations of baseline features or biomarkers assessed using linear regression. Performance of final model(s) will be assessed using r^2 in the case of linear regression, area under the curve (AUC) and Hosmer Lemeshow goodness of-fit test⁵⁵ in the case of logistic regression, or concordance index in the case of Cox proportional hazards regression. AUCs between various models (univariable) will be compared using the method proposed by DeLong et al⁵⁶. For biomarkers, we will create a binary variable (yes/no) depending on whether the % change in mean lesional QSM or K_i during 1-year epochs exceed previously defined respective thresholds (+ 5.8% QSM and +39.6% for K_i)³³ that were significantly associated with new clinical events at high sensitivity and specificity in previously stable lesions. We will then assess the association of this newly created variable (“biomarker event”) with SH rate treated as continuous (using two sample t-test or Wilcoxon rank sum test) and binary (using Chi-square or Fisher’s exact test) outcomes of interest. Finally, we shall compare the sensitivity/specificity of changes in mRS, QOL, and NIHSS scores, and lesional QSM and K_i in relation to SH during the same epochs, using McNemar’s test with SH (yes/no binary) as the reference standard. All tests will be 2-sided and p-values <0.05 considered statistically significant.

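### The Aim 2 phantom criteria, read naturally, do not establish the accuracy, precision or between-site agreement they are named for, and the between-site test still lists three of five FUBV sites

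*Combined protocol and SAP*

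**What the plan says.** Section 9.1 (Specific Aim 2) opens with "This will follow the same design for QSM and DCEQP data acquired using these phantoms", although no such design or phantom is described before it. The next sentence says that a p-value below 0.05 "will be considered a failure, or significant non-zero difference". Three criteria follow.

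- Accuracy, at each FUBV site: r² between observed and known phantom values, with at least 0.95 "needed to validate accuracy of each technique". In addition, Pearson "correlation coefficients r of the FUBV subjects will also be compared using Fisher transformation".
- Precision: "The precision of QSM and DCEQP measurements will be tested by comparing two separate measurements acquired at each site, using a paired t-test", on "7 ferumoxytol concentrations acquired twice by QSM, and 7 permeability values simulated with the phantom twice by DCEQP".
- Reproducibility: "The reproducibility of phantom measurements will be evaluated by comparing the QSM and DCEQP simulation values acquired at New Mexico and Mayo Rochester" with those from Chicago and with each other, by a two-sample t-test.

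No bias limit, CV limit or agreement margin is given. The Year 1 entry of the go/no-go table in section 10.1.2 rejects a technique that misses the validation thresholds at FUBV sites. Section 9.2 lists five FUBV sites: Chicago, New Mexico, Mayo, San Francisco and Johns Hopkins.

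**The concern.** MRI biomarker validation is one of three primary objectives (section 1.1), and section 4.2 identifies multi-site validation as the evidence that is missing. The natural reading is that p<0.05 governs the two t-tests and that r² is a squared correlation. On that reading, each criterion tests something other than its name: linearity instead of accuracy, a mean shift between runs instead of scatter, and failure to reject instead of agreement.

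A technique could then be called validated while one site reads systematically higher than another, or while repeat scans vary more than the plan's own change thresholds allow. Aim 3 defines a biomarker event by whether percent changes "exceed previously defined respective thresholds (+ 5.8% QSM and +39.6% for K_i"), so scatter matters most for QSM. Gain matters where absolute QSM or K_i values, or values pooled across sites, are used. The table in section 10.1.2 also foresees an FDA application for outcome instruments.

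**Working it through.** **Inputs from the plan.** Seven levels, each acquired twice per technique; r² ≥ 0.95; two-sided 0.05 (section 9.1); five FUBV sites (section 9.2). The plan gives no operating characteristic for Aim 2, so there is no figure to reproduce.

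**Inputs assumed.** The documents state neither phantom levels nor scan error. Level sets tried: 0–6, 1–7, 4–10, 10–16, and doubling 1, 2, 4, …, 64. Error is normal and proportional to the level (CV), with 40,000 runs per case.

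**1. Accuracy.** If observed = g × known, then corr(gx, x) = 1 and r² = 1.00 for any g > 0. A site reading half or twice the true value passes. Comparing Pearson r by Fisher transformation is equally unaffected by gain.

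**2. Precision.** The paired statistic is t = mean(d)/(SD(d)/√7), where d is the difference between the two runs. More scatter enlarges numerator and denominator together, so the failure rate does not respond to it. From CV 1% to 30%, an unbiased site passes about 95–97% of the time for evenly spaced levels and 99% for doubling levels. Only the r² gate limits noise (last two columns of the table).

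**3. Reproducibility.** Worked case, levels 1–7, 1.1× gain, no noise, 7 values per site:

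- Means are 4.0 and 4.4, a difference of 0.4. The SD of the levels is 2.160, and 1.1 × 2.160 = 2.376.
- SE = √((2.160² + 2.376²)/7) = 1.214.
- t = 0.4/1.214 = 0.33 on 12 df, p = 0.75.

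The spread of the levels is the error term, so even a noise-free gain passes. Paired figures are for 7 / 14 values per site. Ranges in the last two columns cover r² computed from one scan, from the mean of two, or from all 14 points.

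| Levels | p, 1.1× gain, no noise | p, 1.5× gain, no noise | 1.1× gain flagged, CV 5% | Unbiased site passes paired t and r², CV 5% | Same, CV 10% |
|---|---|---|---|---|---|
| 0–6 | 0.81 / 0.72 | 0.33 / 0.15 | 0 / 0 | – | – |
| 1–7 | 0.75 / 0.63 | 0.20 / 0.056 | 0 / 0 | 96% | about 70–94% |
| 4–10 | 0.57 / 0.40 | 0.035 / 0.002 | 0 / 0 | 89–95% | 9–63% |
| 10–16 | 0.31 / 0.13 | 0.0008 / <0.0001 | <0.1% / 4% | 14–72% | 0–13% |
| doubling | 0.89 / 0.84 | 0.57 / 0.40 | 0 / 0 | 99% | 98–99% |

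A 1.1× gain passes noise-free in every set. A 1.5× gain passes in three sets and is caught in two.

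The alternative on the same scans is to average each site's two scans at a level, take the log ratio between sites at each of the seven levels, and apply a one-sample t-test to the seven values. At CV 5% this flags the 1.1× gain in 98–99% of runs in each of the four sets without a zero level. At CV 10% it flags 55–56%, against 0–2% (7 values) or 0–10% (14 values) for the two-sample test.

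**4. Sites.** Five sites form 5 × 4/2 = 10 pairs; the three named form 3. Section 9.2 also cites 256 CA cases a year at the FUBV sites, and 106 + 80 + 70 = 256 is Chicago, New Mexico and Mayo alone. That suggests a list not updated when the other two joined.

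**The case against.** **The p<0.05 rule.** A reader might infer that the rule cannot be attached to any test. The documents do not support that. Its wording refers to a difference, section 9.1 names two difference tests, and the Aim 3 text sets two-sided 0.05 for all tests. What remains is a missing antecedent, which one sentence repairs.

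**Other readings.** If r² meant agreement with the identity line, or p<0.05 applied to observed minus known values, one might infer that gain would mostly be seen. That does not hold generally. At 1.1× without noise, 1 − SS(observed − known)/SS(known about its mean) is 0.967, 0.95, 0.867, 0.567 and 0.983 for the five sets in table order, so three sets pass or sit at the limit. An observed-minus-known t-test at CV 5% flags the 1.1× site in 90–100% of runs for levels 1–7, 4–10 and 10–16, but in only 13–14% for doubling levels.

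**Size depends on assumptions.** This stands. With bunched levels the existing r² gate is already strict on noise, and a large gain can be caught. That all sites scan the same nominal levels is also an inference.

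**The two added sites.** It is tempting to say they go unvalidated. They do not: the accuracy and precision checks are planned at each FUBV site. Only the between-site list is short.

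**Consequences.** One might infer that a chance failure at any single site rejects a technique, or that phantom noise gives a rate of false biomarker events in patients. The documents state no any-site rule and do not show that lesion error equals phantom error, so neither can be sized.

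**Safeguards.** Statisticians are to refine each aim's plan in year 1 (section 10.1.4). Section 10.1.2 adds imaging-core validation, a midterm quality threshold and a cross-site consistency check in years 3–4. Aim 3 compares biomarker change with observed bleeding. These soften the gap, but none states a criterion for gain or scatter.

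**Conclusion.** The mismatch between criterion and property is real and should be fixed. That r² ignores gain, that the paired test ignores scatter, and that p ≥ 0.05 does not show agreement follow from the methods and need no assumed input. The sizes do rest on assumed levels and error: a 10% between-site gain is flagged in 0–4% of runs at CV 5%, against 98–99% for a level-paired analysis.

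The harm is bounded. Recurrent bleeding, the Aim 3 primary endpoint, does not depend on the phantom work, and percent change within a patient cancels a gain that stays stable. What is exposed is the meaning of the validated label, and any use of absolute or pooled biomarker values. The three-site list is a smaller matter of updating.

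**What to change.** Amend section 9.1 (Aim 2) and re-analyse the phantom scans already planned.

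- **Wording.** State in one line that p<0.05 refers to the difference tests, and which r² is meant.
- **Accuracy.** Keep r² ≥ 0.95 as a linearity check. Add a gain estimate against known values with its CI: the mean log ratio at non-zero levels, or slope and intercept where levels are well spread. With a log-ratio margin of 1.10 (90% CI), an unbiased site passes in 100% of runs at CV 5% and about 86% at CV 10%; a 1.2× site passes in fewer than 0.1%. Do not default to a slope margin of 0.85–1.15: at CV 5% unbiased sites meet it in 98%, 62% and 3% of runs for levels 1–7, 4–10 and 10–16.
- **Precision.** Replace the paired t-test as the criterion by the within-level CV and the repeatability coefficient (1.96 × √2 × CV = 2.77 × CV), with CIs, reported beside 5.8% for QSM and 39.6% for K_i. Seven pairs give a 95% CI of 0.66 to 2.04 times the estimated CV, so do not require the QSM upper limit to fall below 5.8%. With a one-sided 95% factor of 1.80, that would need an observed CV of about 5.8/(1.80 × 2.77) = 1.2%.
- **Reproducibility.** Replace the two-sample t-test by a level-paired log ratio with a 90% CI against a pre-stated equivalence margin, at all five FUBV sites. If nominal levels differ between sites, compare each site's observed/known ratios. Handle zero levels separately.
- **Margins.** Set them once the levels are stated, and to what seven levels scanned twice can support.

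**Cost.** SAP wording and a short re-analysis; no new scans, provided nominal levels are shared or known. The downside is that some noisy but unbiased sites will miss a tight margin: at CV 10%, a 1.10 between-site margin is met in about 46% of runs and a 1.15 margin in about 88%.

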3 OBJECTIVES AND ENDPOINTS

Specific Aim 1: To harmonize data entry, and assess prospective enrollment rates and baseline characteristics of CASH cases at multiple high volume sites with clinical interest in CAs.

Specific Aim 2: To test the feasibility, accuracy, precision and reproducibility of MRI biomarker measurements at multiple sites, critical to their potential application as predictive, diagnostic or outcome measures.

Specific Aim 3: To assess rates of symptomatic hemorrhage and changes in biomarkers and functional status/QOL measures during prospective follow-up.

Specific milestones are proposed and go/no-go decisions based on interim analyses and results of these aims. Data from this project will insure the most stringent rigor in trial assumptions, including validated enrollment rates and baseline features specific to CASH. Results will endorse or reject outcome instruments or biomarkers based on empiric observations, hypothesizing a clinically meaningful impact of putative therapies.

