5.1 INCLUSION CRITERIA

- (1) 18 years of age and older.
- (2) diagnosed with a brain CA (single or multiple).
- (3) had a SH within the past year (with demonstrated new lesional bleeding or hemorrhagic growth >3mm on diagnostic studies AND attributable new symptoms).
- (4) ~~no prior treatment of the symptomatic lesion (after neurosurgical consultation)~~. Subject is able to provide informed consent.

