8 STUDY ASSESSMENTS AND PROCEDURES

All eligible subjects will be identified by the study team at each site. Based on clinic schedules and current patient databases, all CCM patients with a symptomatic hemorrhage within the last 12 months (of screening) are eligible for the trial. Sites will screen neurology, neurosurgery, and neurointerventional radiology clinic schedules, MRI schedules, and attend Neurovascular rounds to help identify potential subjects. Additionally, study sites will rely on referrals from the various services listed above, or self-referrals via web searches and through the Angioma Alliance, a patient support group. Once identified, the study coordinator at each site, along with the site PI, will screen the subject for basic eligibility. Screened subjects not scheduled to come in for a clinical visit within their eligibility window will be contacted by the study coordinator or PI to explain the study and determine if the subject is interested. When the subject comes in, either for a standard clinic visit or for a study visit, the study team will review the subject's medical history to ensure the subject meets the inclusion criteria. The trial will be explained and informed consent obtained. After consent is obtained a physical exam (height, weight, vital signs) will be completed, a baseline modified Rankin Score obtained, and EQ-5D, PROMIS 29, and NIH stroke scale assessments completed. The study team will also collect information about the subject's history, pertinent to the disease (history of seizure, resection of other lesions, etc.). All subjects at the FUBV sites (enrolled to the FUBV arm) will have a MRI scan including the additional sequences for research as specified in Specific Aim 2 (QSM/DCEQP). All women of childbearing age will undergo a urine or serum beta-HCG pregnancy test prior to MRI to confirm no pregnancy, per local institutional guidelines.

Subjects enrolled in the FUBV arm will return for 2 follow up visits: one at 12 months and the other at 24 months. Excluding the informed consent process, all baseline procedures will be repeated. Subjects will have completed their participation upon completion of the baseline visit procedures (SCA arm) or the year 2 visit (FUBV arm). All subjects enrolled in the SCA arm will have one study visit only.

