Specific Aim 3. Time to recurrent SH will be analyzed using Kaplan Meier method and Cox proportional hazards regression approach. Rates of recurrent SH/patient/year from initial SH qualifying event, and SH/patient/year from enrollment (potentially more relevant for trial modeling) will be estimated along with 95% CIs. Changes in mean lesional QSM and K_i during 1 and 2-year epochs will be compared using paired t-test or Wilcoxon signed rank test to assess changes within patients over time, including 95% CIs. To test predictive, monitoring or surrogate outcome hypotheses, two sample t-test or Wilcoxon rank sum test will be used to compare such changes between patients with and without recurrent SH. Categorical variables such as proportions of patients with a drop in mRS score ≥ 1 point, difference in EQ-5D and PROMIS 29 scores, NIHSS scores, between patients with and without recurrent SH will be compared using Chi-square or Fisher's exact test. Associations of baseline characteristics (sex, lesion locations, familial/sporadic) and recurrent SH as a binary outcome (yes/no) will be assessed using

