Follow-up and Biomarker Validation (FUBV) Sites: University of Chicago, University of New Mexico, Mayo, University of California San Francisco, and Johns Hopkins were chosen because of additional established infrastructure for advanced imaging, including identified MRI physicists, neuroradiologists and site engineers who will work with the Biomarker Imaging Core (BIC) on implementing QSM and DCEQP protocols. A subset of approximately 120 CASH cases will be enrolled at FUBV sites to perform imaging biomarker validation studies (Specific Aim 2) and follow-up of CASH cases annually for up to two years (Specific Aim 3) to evaluate changes in outcomes. This subset of CASH cases will undergo a research MRI scan at baseline and at 1 and 2-year follow-up visits and undergo modified Rankin Scale (mRS) score and EQ-5D, PROMIS 29, and NIHSS assessments. A target recruitment of 120 CASH cases over 3-4 years at the sites conducting the FUBV arm is amply justified, with demonstrated 256 CA cases recently evaluated per year at those sites, expecting to identify 38 CASH cases each year (15% prevalence). Utah and Barrow may also serve as alternate FUBV arm sites if needed, with large demonstrated CA clinical activity. The University of California San Francisco and Johns Hopkins are now part of the FUBV arm.

Assuming a sample size of 120 CASH cases, and allowing 30% dropouts or missing biomarker or other data, we would have 84 evaluable patients (168 patient-years). We project 10%-20% re-bleed rate/year, supported by population studies and meta-analyses of CASH^{18, 19}, with the higher estimate particularly applying to brainstem cases. We would hence expect 17-34 SHs. Based on this, for continuous outcomes we will have 80% power at an alpha level of 0.05, to detect a difference between the means of patients with and without re-bleeding of at least 0.63-0.77 standard deviation. For categorical outcomes (i.e. presence or absence of a risk factor) we will be able to detect a difference of 32-40% between these two groups. This allows testing of questions regarding the rate of SH, and the prevalence of other outcomes in relation to SH during follow-up (Specific Aim 3).

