9.4 STATISTICAL ANALYSES

9.4.1 GENERAL APPROACH

Data collection. Key variables to be collected in this study will be decided on by all stakeholders in Year 1. At a minimum, these will include patient demographics, genotype, baseline MRI lesion features of the hemorrhagic CA (size, location), time from SH, prior bleeds/dates, and diagnosis date. Functional status will be measured using the modified Rankin Scale (mRS) score⁵⁷, Euro-QoL⁵³, PROMIS29⁵², and NIH Stroke Scale. PROMIS 29 short forms are an assessment of anxiety, depression, and fatigue, and have been validated for use in several common neurological disorders. Presence of obstructive sleep apnea. Recent findings suggest that sleep apnea results in decreased blood flow to the brain. This transient ischemia may be implicated in CA hemorrhage. Sleep apnea questions will be included in the dataset and response analyses as described under the topic Predictors of SH.

Data harmonization. Common data elements from each site will be reviewed, updated, and harmonized using an iterative, stepwise process based on DataSHaPER (DataSchema and Harmonization Platform for Epidemiologic Research) recommendations⁵⁸⁻⁶⁰. Questionnaires, codebooks, and protocols, etc. at the 3 established CA databases (Table 2) will be compiled and distributed for review. A series of Executive Committee teleconference calls will be held in Year 1 to decide on a set of 'target' data elements for potential clinical trials, as has been similarly done with the consensus process for developing clinical guidelines paper¹⁷. The EDHC and DCC will then develop standardized electronic data entry forms and codebooks for data collection. Each site shall be trained in abstracting and entering data for their cases online. Data will be collected prospectively in Years 2-5. Analysis datasets will be generated quarterly by the DCC for quality control analysis by EDHC.

Event Rate: Time to recurrent SH will be analyzed using Kaplan Meier method and Cox proportional hazards regression approach. Rates of recurrent SH/patient/year from initial SH qualifying event, and SH/patient/year from enrollment (potentially more relevant for trial modeling) will be estimated along with 95% CIs.

Biomarker changes over 2 years: Changes in mRS, EQ-5D, PROMIS 29, and NIHSS scores, mean lesional QSM and K_i during 1 and 2-year epochs will be compared using paired t-test or Wilcoxon signed rank test to assess changes within patients over time, including 95% CIs.

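### The recurrent-SH rate counted from the qualifying SH has no risk-set entry rule and no rule for re-bleeds before enrolment, so it can be biased in either direction

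*Combined protocol and SAP*

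**What the plan says.** Section 9.1 (Specific Aim 3) and Section 9.4.1 (Event Rate) carry the same two sentences. The first is "Time to recurrent SH will be analyzed using Kaplan Meier method and Cox proportional hazards regression approach", with no time origin. The second names two origins: "Rates of recurrent SH/patient/year from initial SH qualifying event, and SH/patient/year from enrollment (potentially more relevant for trial modeling) will be estimated", with 95% CIs.

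The entry conditions are these:

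- Section 5.1 requires that the patient "had a SH within the past year". Section 8 anchors the window to screening: "all CCM patients with a symptomatic hemorrhage within the last 12 months (of screening) are eligible for the trial".
- The synopsis limits the population to bleeding lesions not excised or irradiated. Item 4 of Section 5.2 concerns prior or planned treatment of the symptomatic lesion.

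On what is counted, the synopsis gives the primary endpoint as recurrent bleeding during follow-up, and Section 3 words Aim 3 as "To assess rates of symptomatic hemorrhage and changes in biomarkers and functional status/QOL measures during prospective follow-up". Section 9.4.1 lists among the baseline variables "time from SH, prior bleeds/dates, and diagnosis date", but attaches no analysis rule to them.

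No section says when a patient joins the risk set on the SH clock, whether the interval from SH to enrolment is person-time, or whether a re-bleed in that interval is an event.

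**The concern.** A patient is observed prospectively only from enrolment, but the SH clock starts up to about a year earlier. To be enrolled, the patient must have reached enrolment with the lesion still untreated. Time before enrolment is therefore either time in which no follow-up event can occur, or time seen only in patients selected for entry. Put into a denominator without an entry rule, it distorts the rate.

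This goes beyond missing detail. With delayed entry at enrolment, the overall SH-origin rate has the same events and the same person-time as the enrolment-origin rate, so the two are identical. Two distinct overall rates can arise only if time before enrolment is used in some way, and the plan does not say how.

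At stake is the interpretation of a primary objective. The study would report two recurrent-SH rates from the same patients. If the SH-origin rate is the lower one only because of the lag, a reader could conclude that risk is lower soon after an SH and rises later.

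**Working it through.** **Inputs from Section 9.2.** 120 FUBV patients, 30% loss, two years of follow-up, 10%-20% re-bleeds per year. The lag from SH to enrolment is not given anywhere; only its limit of about one year follows from eligibility. Mean lags (L) of 1, 3 and 6 months are my assumptions.

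**Step 1: reproduce the plan's figures.** 120 × 0.70 = 84 patients; 84 × 2 = 168 patient-years; 168 × 0.10 = 16.8 and 168 × 0.20 = 33.6. This agrees with "We would hence expect 17-34 SHs". Using the rounded counts, the enrolment-origin rate is 17/168 = 10.1% to 34/168 = 20.2% per year.

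**Step 2: follow-up SHs only, over time since the SH.** Patient-years = 84 × (2 + L). The rate is the enrolment-origin rate × 2/(2 + L).

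| Mean lag (assumed) | Patient-years | 17 SHs | 34 SHs | Factor | Shortfall |
|---|---|---|---|---|---|
| 0 | 168 | 10.1% | 20.2% | 1.00 | none |
| 1 month | 175 | 9.7% | 19.4% | 0.96 | 4% |
| 3 months | 189 | 9.0% | 18.0% | 0.89 | 11% |
| 6 months | 210 | 8.1% | 16.2% | 0.80 | 20% |

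A mean lag of a full year, about the most that eligibility allows, would give 84 × 3 = 252 patient-years and a 33% shortfall.

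**Step 3: all SHs after the qualifying one, over time since it.** Let m be how likely a patient with a pre-enrolment re-bleed is to enter, relative to a patient without one. To a close approximation, the rate is the true rate × (m × L + 2)/(L + 2). Take L = 0.5 years and an assumed true rate of 0.15 per year:

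- m = 1 (entry unrelated to re-bleeding): 2.5/2.5, giving 0.150, no bias.
- m = 0.75 or 0.5 (some re-bleeders treated before entry): 2.375/2.5 and 2.25/2.5, giving 0.143 and 0.135, 5% and 10% low.
- m = 1.5 or 2 (re-bleeds bring patients to the centres): 2.75/2.5 and 3/2.5, giving 0.165 and 0.180, 10% and 20% high.

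The documents give no value for m. Section 2.2 says lesions are usually excised after one or more hemorrhagic strokes, which makes m below 1 plausible. Section 8 recruits from specialty clinics, rounds, referrals and self-referrals, which makes m above 1 plausible too.

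**Step 4: delayed entry.** Person-time starts at enrolment, so the same 17-34 SHs fall over 168 patient-years and the rate is again 10.1-20.2%.

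**The case against.** The strongest reply is that the plan is silent, not wrong. It defines neither numerator nor denominator for the SH-origin rate. The plural could mean rates tabulated by time since SH, which would differ from the enrolment rate even with correct delayed entry. Bleed dates are collected, so a matched numerator and denominator is possible. This stands in part: the 4-20% shortfall belongs to one reading, under assumed lags, and is not a planned error. It does not remove the problem, because the matched version is unbiased only if m = 1, which untreated-lesion eligibility gives no reason to expect.

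Four stronger readings are tempting and are not supported:

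- *The rate will be understated.* Step 3 shows that the bias can run upward.
- *The Kaplan-Meier curve will be badly biased.* If it were run on the SH clock without delayed entry, with lags uniform over 0-12 months and λ = 0.15 per year, 1-year recurrence would read 1 - (1 - e^-λ)/λ = 7.1% against a true 1 - e^-λ = 13.9%. At 2 years it would read about 20% against 25.9%. But the plan chooses no origin for the curve, and an endpoint set during follow-up makes enrolment the natural one.
- *Future trials will be mis-sized.* Section 9.1 itself marks the enrolment rate as possibly the better one for trial modelling, and no sample size uses the SH-origin rate. The Year 2 decision point in Section 10.1.2 on visit timing refers to the timing and rate of recurrent SH, but names no origin.
- *The qualifying SH is undefined.* Where several SHs fall in the window, the word for initial points to the earliest. A clarifying clause would do no harm, but this is not the defect.

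The bias is also modest beside sampling error. Exact 95% CIs for the enrolment rate are 0.059-0.162 (17 SHs) and 0.140-0.283 (34 SHs), and the 6-month values of 0.081 and 0.162 lie inside them. That limits the practical weight of the point. It does not make the gap between the two rates interpretable, since both come from the same patients and the lag alone can produce it.

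**Conclusion.** The point holds in a limited form. Taken literally, the SH-origin rate is biased because no rule governs entry into the risk set or re-bleeds before enrolment. With follow-up SHs only, it falls below the enrolment rate by the factor 2/(2 + mean lag): 4%, 11% and 20% at assumed mean lags of 1, 3 and 6 months. That is also the shortfall from the truth if the re-bleed rate is constant over time. With pre-enrolment re-bleeds counted, the bias is zero, negative or positive according to how re-bleeding affects entry, which the documents do not quantify.

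Not affected are the enrolment-origin rate, the comparison of study years 1 and 2, and the figures in Section 9.2 (84 patients, 168 patient-years, 17-34 SHs and the detectable differences). Severity is minor to should-fix.

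**What to change.** In Section 9.1 (Specific Aim 3) and Section 9.4.1 (Event Rate):

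1. State enrolment as time zero for the main recurrent-SH rate, Kaplan-Meier and Cox, counting SHs after enrolment.
2. For any time-since-SH result, enter each patient into the risk set at enrolment (delayed entry). Present it in coarse, yearly bands, because the overall delayed-entry rate only repeats the enrolment rate.
3. Report the interval from SH to enrolment, and the re-bleeds within it, descriptively.

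The cost is a few sentences and an entry-time argument in the code. The dates needed are already collected.

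The downside is sparse early information. With 84 patients, an assumed uniform lag of 0-12 months and 0.15 per year, months 0-3 after the SH hold 84 × 0.25²/2 = 2.6 person-years, or 0.4 expected re-bleeds. The first year holds about 40 person-years (84 × 0.5 = 42, less time after a first re-bleed), or 6 expected. Delayed entry also cannot recover patients treated before they could enrol, so the result applies only to those who reach enrolment with an untreated lesion. The report should say so.
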